#### **HAQ®-DI (for subjects with PSA at baseline of the core study)**

Summary statistics will be derived for HAQ®-DI score over time for all subjects with psoriatic arthritis recorded on the Psoriatic Arthritis History eCRF at screening visit of the core study.

Absolute and relative frequencies for HAQ®-DI response will also be presented. HAQ®-DI response is defined by an improvement of 0.3 score points compared to baseline.

#### **9.5.4 Pharmacokinetics**

All completed subjects with quantifiable PK measurements of secukinumab will be included in the PK data analysis. Serum concentrations will be expressed in mass per volume units. All concentrations below the limit of quantification or missing data will be labeled as such in the concentration data listings. PK concentrations will be summarized by visit and treatment group. In addition to mean, standard deviation, coefficient of variation, median and quartiles, the geometric mean and geometric coefficient of variation and n(log) will be presented.

#### **9.5.6 Biomarkers**

Not applicable.

#### **9.6 Interim analyses**

One interim analysis is planned for this study. At time of marketing authorization submission of the AIN457A project blinded safety data of this study will be reported.

A PEA is planned to be performed when all subjects have completed the visit at which the primary endpoint is assessed (Week 68). At this time point, the Sponsor will be unblinded, whereas investigators and study participants will remain blinded.

All data collected up to Week 68 will be analyzed.

Additional interim analyses may be conducted at various time points for publications or health authority requests. The study procedures will not be modified as a result of these interim analyses

## 9.7 Sample size calculation

**Assumptions for the number of subjects eligible for randomized withdrawal (i.e for the analysis of primary endpoint):**

- Drop-out rate on secukinumab at Week 12 in core studies: 5% (estimate from CAIN457A2211)
- Drop-out rate on placebo at Week 12 in core studies: 15% (from CAIN457A2211)
- Placebo PASI 75 response rate at Week 12: 5% (conservative assumption)
- Drop-out rate on secukinumab up to Week 52 in core studies: 15% (common for secukinumab induction and placebo induction regimens, as in [Leonardi et al, 2008](#))
- PASI 75 response rate at Week 52 on secukinumab 150 mg in core studies: 65% (from dosing rationale in protocols of core studies) (power would be larger for 300 mg if we would assume similar loss of PASI75 rates)
- Type-I-error rate is defined to one-sided 2.5%

With these assumptions it is estimated to have 414 subjects eligible per dose to enter the randomized withdrawal, with a randomization ratio of 2:1 this would be 276 subjects on 150 mg and 138 subjects on placebo. With about 400 subjects the study would have more than 90% power to detect differences in the cumulative rates if 10% of subjects on secukinumab lost PASI 75 response versus 23% on placebo, PASS 2008 software (Log Rank Survival Power Analysis - Simple).

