### Testing strategy

The familywise error will be set to  $\alpha=2.5\%$  (one-sided). The two hypotheses  $H_1$  (referring to 150 mg) and  $H_2$  (referring to 300 mg) will be tested at  $\alpha/2=1.25\%$  one-sided. In case, a null hypothesis has been rejected for one dose, but not for the other dose, the alpha can be shifted to the other dose and the null hypotheses can be retested at level  $\alpha=2.5\%$  (one-sided). The graphical approach of [Bretz et al (2009)] for sequentially rejective testing procedures is used to illustrate the testing strategy (Figure 9-1):

**Figure 9-1** Testing strategy

Other secondary endpoints will not be included in the testing strategy.

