## 1.9.3 Testing strategy

The family wise error will be set to  $\alpha$ =2.5% (one-sided). The two hypotheses H1 (referring to 150 mg) and H2 (referring to 300 mg) will be tested at  $\alpha$ /2=1.25% one-sided. In case, a null hypothesis has been rejected for one dose, but not for the other dose, the alpha can be shifted to the other dose and the null hypotheses can be retested at level  $\alpha$ =2.5% (one-sided).

The graphical approach of Bretz et al. 2009 for sequentially rejective testing procedures is used to illustrate the testing strategy:

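### The power of more than 90% is stated at one-sided 2.5%, but each dose is first tested at one-sided 1.25%, where more than 90% is not assured (about 84–90% with 400 subjects)

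*Protocol*

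**What the plan says.** The sample size section (Protocol 9.7, repeated in SAP 1.11) gives as an assumption "Type-I-error rate is defined to one-sided 2.5" per cent. On numbers, "it is estimated to have 414 subjects eligible per dose to enter the randomized withdrawal", and "with a randomization ratio of 2:1 this would be 276 subjects on 150 mg and 138 subjects on placebo". The claim itself is: "With about 400 subjects the study would have more than 90% power to detect differences in the cumulative rates", where the difference is that "10% of subjects on secukinumab lost PASI 75 response versus 23% on placebo". The method is given only as "PASS 2008 software (Log Rank Survival Power Analysis - Simple".

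The 276/138 split shows that this is the power of one dose comparison. Protocol 9.4.2 confirms that each dose is compared with its own placebo group and that the two placebo groups are not pooled.

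The testing strategy (Protocol synopsis, Protocol 9.4.2, SAP 1.9.3) sets the family-wise error at one-sided 2.5%. It then says "The two hypotheses H1 (referring to 150 mg) and H2 (referring to 300 mg) will be tested at" half of that, one-sided 1.25%. If one dose is rejected and the other is not, "the alpha can be shifted to the other dose and the null hypotheses can be retested at level" 2.5%.

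Neither sample size section mentions the 1.25% level, gives power at that level, or says that the claim relies on the alpha shift. The drop-out rates listed there all concern the core studies up to Week 52; none covers Week 52 to Week 68.

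**The concern.** The power of a single comparison is stated at the level of the whole family. That is not the level at which either dose is tested first. A dose has 2.5% available only if the other dose has already been rejected, so power at 2.5% for one dose is conditional on success elsewhere, and the text does not say so.

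What is at stake is how the design is described. Someone judging the chance that a given dose succeeds on its own would read more than 90%, when the figure at the first step may lie several points lower. The test and its error control are not in question.

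**Working it through.** **Inputs.** Cumulative loss 10% (secukinumab) and 23% (placebo), 2:1 allocation, N = 400 (the number in the power sentence) or 414 (the number expected), one-sided log-rank test: all from Protocol 9.7. Levels 2.5% and 1.25%: Protocol 9.4.2 and SAP 1.9.3. Critical values are 1.960 and 2.241.

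**Hazard ratio and events.** HR = ln(0.90)/ln(0.77) = 0.1054/0.2614 = 0.403, so |ln HR| = 0.9085. The average event proportion is (0.23 + 2 × 0.10)/3 = 0.1433, giving 57.3 events for N = 400 and 59.3 for N = 414.

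**Formulas.** Power is Φ(Z − critical value), with
- Schoenfeld: Z = √(events × 2/3 × 1/3) × |ln HR|. For N = 400, √12.74 × 0.9085 = 3.243; for N = 414, 3.299.
- Freedman: Z = √(2 × events) × (1 − HR)/(1 + 2 HR). For N = 400, 10.71 × 0.597/1.806 = 3.539; for N = 414, 3.600.
- Simulation: log-rank test on visits at Weeks 56, 60, 64 and 68, constant hazard, no drop-out, no stratification, 200,000 runs.

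**The plan's figure at 2.5%, then the same calculation at 1.25%.**

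| | N = 400, 2.5% | N = 400, 1.25% | N = 414, 2.5% | N = 414, 1.25% |
|---|---|---|---|---|
| Schoenfeld | 90.0% | 84.2% | 91.0% | 85.5% |
| Simulated log-rank | 92.8% | 88.6% | 93.5% | 89.6% |
| Freedman | 94.3% | 90.3% | 94.9% | 91.3% |

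Example: Schoenfeld, N = 400, is Φ(3.243 − 1.960) = Φ(1.283) = 90.0% and Φ(3.243 − 2.241) = Φ(1.002) = 84.2%. With whole subjects (133/267) the latter is 84.1%. Repeated simulations at 1.25% gave 88.3–88.6% for N = 400 and 89.3–89.6% for N = 414, so about 89% in both cases. The plan's figure is reproduced at 2.5%, only just so under Schoenfeld with 400 subjects.

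**After the alpha shift.** Assume that both doses have the same effect and the same number of subjects. The comparisons share no subjects, so they are independent. With p₁ the power at 2.5% and p₂ the power at 1.25%:
- A given dose: p₂ + (p₁ − p₂) × p₂. From the simulated values, N = 400: 0.886 + 0.042 × 0.886 = 92.3%; N = 414: 0.896 + 0.039 × 0.896 = 93.1%.
- Both doses: 2p₁p₂ − p₂². N = 400: 1.644 − 0.785 = 85.9%; N = 414: 1.676 − 0.803 = 87.3%.

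The same arithmetic with the formula values gives, for a given dose, 89.1% (Schoenfeld, N = 400) to 94.6% (Freedman, N = 414), and for both doses 80.7% to 90.0%.

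**Loss between Week 52 and Week 68.** The documents give no rate, so 5%, 10% and 15% are assumptions. Reducing the number of subjects by these shares (a somewhat pessimistic treatment, since a censored subject still contributes some follow-up), power at 1.25% is:

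| Assumed loss | N = 400, Schoenfeld to Freedman | N = 414, Schoenfeld to Freedman |
|---|---|---|
| 5% | 82.1–88.6% | 83.5–89.8% |
| 10% | 79.8–86.8% | 81.3–88.0% |
| 15% | 77.3–84.6% | 78.8–85.9% |

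**The case against.** The strongest reply is that nothing stated has been shown to be false. The arithmetic at 2.5% is right. The documents name a software procedure but no formula, and under Freedman the power at 1.25% is still 90.3% with 400 subjects and 91.3% with 414. The planned procedure includes the alpha shift; if both doses work equally well, simulated per-dose power is about 92–93%, in line with the claim. The sentence speaks of the study and makes no claim about winning on both doses. Power to win on at least one dose at the first step, 1 − (1 − p₂)², is 97.5% (Schoenfeld, N = 400) to 99.2% (Freedman, N = 414).

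Much of this stands. A reader might infer that the study is underpowered or that more than 90% is wrong; the documents do not support either. A reader might also infer that the plan promises 93–94% per dose; it says only more than 90%. Basing the power sentence on about 400 when 414 are expected leaves a small margin, 14/414 = 3.4%.

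The assumed difference may also be cautious. Protocol 3.3 expects around 40% of subjects to have lost PASI 75 response 16 weeks after the last dose. With 10% versus 40% (HR 0.206, 80 events for N = 400), power at 1.25% exceeds 99.9% under both formulas. That bears on the power in practice; it does not repair a statement that Protocol 9.7 bases on 23%.

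What does not fall away is the mismatch itself. The claim needs either a favourable formula or success on the other dose, and the text discloses neither condition. Under Schoenfeld with 400 subjects, even the alpha shift leaves per-dose power at 89.1%.

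**Conclusion.** The point holds as a correction to a stated figure. At the level of the first test, the loss against the stated level is about 4 to 6 percentage points, taking per-dose power to about 84–90% with 400 subjects and about 85–91% with 414. These figures rest on the plan's own 10% versus 23%, proportional hazards, 2:1 allocation and no loss after Week 52. The figures after the alpha shift rest in addition on equal effects in the two doses.

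It would go too far to conclude that the primary test is invalid or that more subjects were needed. The family-wise error is controlled as specified. The Amendment 2 section of the protocol reports recruitment as complete with 1146 randomized. SAP 1.1 says that the Week 68 primary analysis will not be performed again in the final analysis. No decision about the test or the sample size hangs on this.

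**What to change.** In Protocol 9.7 and SAP 1.11:
- Name the formula behind the software procedure.
- Restate per-dose power at one-sided 1.25%: about 84–90% for 400 subjects and about 85–91% for 414, or the single value once the formula is named.
- Give separately, under the stated assumption that both doses have the same effect, about 92–93% per dose after the alpha shift and about 86–87% for both doses (simulated values; recompute them if a formula is adopted).
- Say that no loss between Week 52 and Week 68 is assumed, or show power over a range of assumed loss.

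Sample size, test and alpha do not change. The cost is a few sentences in each document and a slightly less favourable stated figure.

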## 10 Ethical considerations

### 10.1 Regulatory and ethical compliance

This clinical study was designed and shall be implemented and reported in accordance with the ICH Harmonized Tripartite Guidelines for Good Clinical Practice, with applicable local regulations (including European Directive 2001/20/EC, US Code of Federal Regulations Title 21, and Japanese Ministry of Health, Labor, and Welfare), and with the ethical principles laid down in the Declaration of Helsinki.

### 10.2 Informed consent procedures

Eligible subjects may only be included in the study after providing written (witnessed, where required by law or regulation), IRB/IEC-approved informed consent, or, if incapable of doing so, after such consent has been provided by a legally acceptable representative of the subject. In cases where the subject's representative gives consent, the subject should be informed about the study to the extent possible given his/her understanding. If the subject is capable of doing so, he/she should indicate assent by personally signing and dating the written informed consent

document or a separate assent form. Informed consent must be obtained before conducting any study-specific procedures (i.e. all of the procedures described in the protocol). The process of obtaining informed consent should be documented in the subject source documents.

Novartis will provide to investigators in a separate document a proposed informed consent form that complies with the ICH GCP guideline and regulatory requirements and is considered appropriate for this study. Any changes to the proposed consent form suggested by the investigator must be agreed to by Novartis before submission to the IRB/IEC, and a copy of the approved version must be provided to the Novartis monitor after IRB/IEC approval.

Women of child bearing potential should be informed that taking the study treatment may involve unknown risks to the fetus if pregnancy were to occur during the study and agree that in order to participate in the study they must adhere to the contraception requirement for the duration of the study. If there is any question that the subject will not reliably comply, they should not be entered in the study.

### **10.3 Responsibilities of the investigator and IRB/IEC**

The protocol and the proposed informed consent form must be reviewed and approved by a properly constituted IRB/IEC before study start. A signed and dated statement that the protocol and informed consent have been approved by the IRB/IEC must be given to Novartis before study initiation. Prior to study start, the investigator is required to sign a protocol signature page confirming his/her agreement to conduct the study in accordance with these documents and all of the instructions and procedures found in this protocol and to give access to all relevant data and records to Novartis monitors, auditors, Novartis Clinical Quality Assurance representatives, designated agents of Novartis, IRBs/IECs/REBs, and regulatory authorities as required. If an inspection of the clinical site is requested by a regulatory authority, the investigator must inform Novartis immediately that this request has been made.

### **10.4 Publication of study protocol and results**

Novartis assures that the key design elements of this protocol will be posted in a publicly accessible database such as [clinicaltrials.gov](http://clinicaltrials.gov). In addition, upon study completion and finalization of the study report the results of this trial will be either submitted for publication and/or posted in a publicly accessible database of clinical trial results.

## **11 Protocol adherence**

Investigators ascertain they will apply due diligence to avoid protocol deviations. Under no circumstances should the investigator contact Novartis or its agents, if any, monitoring the trial to request approval of a protocol deviation, as requests to approve deviations will not be granted.

This protocol defines the study objectives, the study procedures and the data to be collected on study participants. Under no circumstances should an investigator collect additional data or conduct any additional procedures for any research related purpose involving any investigational drugs.

If the investigator feels a protocol deviation would improve the conduct of the study this must be considered a protocol amendment, and unless such an amendment is agreed upon by Novartis

and approved by the IRB/IEC it cannot be implemented. All significant protocol deviations will be recorded and reported in the CSR.

## 11.1 Protocol Amendments

Any change or addition to the protocol can only be made in a written protocol amendment that must be approved by Novartis, Health Authorities where required, and the IRB/IEC. Only amendments that are required for subject safety may be implemented prior to IRB/IEC approval. Notwithstanding the need for approval of formal protocol amendments, the investigator is expected to take any immediate action required for the safety of any subject included in this study, even if this action represents a deviation from the protocol. In such cases, Novartis should be notified of this action and the IRB/IEC at the study site should be informed within 10 working days.

## 13 Appendices

### 13.1 Appendix 1: Clinically notable laboratory values and vital signs

The following criteria will be used to define expanded limits and notable abnormalities of keylaboratory tests. Notable values for blood pressure and pulse are presented in [Section 6.5.2](#). Whether action needs to be taken to address notable laboratory or vital signs values will be decided by the investigator, taking into account the overall status of the subject. No specific action is foreseen as part of the study protocol.

#### Liver Function and Related Variables

Alanine transaminase (ALT) (SGPT):	> 3 x Upper Limit of Normal (ULN)
Aspartate transaminase (AST) (SGOT):	> 3 x ULN
Total bilirubin:	> 2 x ULN
Alkaline phosphatase:	> 2.5 x ULN

#### Renal Function and Electrolyte Variables

Creatinine (serum):	> 1.5 x ULN
Potassium:	> 6 mmol/L or < 3 mmol/L
Sodium:	> 160 mmol/L or < 115 mmol/L

#### Hematology Variables

Hemoglobin:	≥ 20 g/dL decrease from baseline
Platelet count:	< Lower Limit of Normal (LLN)
White blood cell count:	< 0.8 x LLN
Neutrophils	< 0.9 x LLN
Eosinophils	> 1.1 x ULN
Lymphocytes	> 1.1 x ULN

#### Urinalysis Variable

Protein urine dipstick:	++*
-------------------------	-----

\* ++ is ≥ 100 mg/dL

## 13.2 Appendix 2: Blood collection log for pharmacokinetics (PK) and immunogenicity (IG)

**Table 13-1 Blood collection log for PK**

Visit Name	Time point	Volume (approx.)	Analyte	Sample number	PK collection number**
Week 52 	Pre-dose	(2 mL)	AIN457 for PK	(5)	(5)
Week 56	Pre-dose	2 mL	AIN457 for PK	6	5
Week 60	Pre-dose	2 mL	AIN457 for PK	7	5
Week 64 	Pre-dose	2 mL	AIN457 for PK	8	5
Week 68	Pre-dose	2 mL	AIN457 for PK	9	5
Week 72	Pre-dose	2 mL	AIN457 for PK	10	5
Week 76 	Pre-dose	2 mL	AIN457 for PK	11	5
Week 80	Pre-dose	2 mL	AIN457 for PK	12	5
Week 84	Pre-dose	2 mL	AIN457 for PK	13	5
Week 88 	Pre-dose	2 mL	AIN457 for PK	14	5
Week 92	Pre-dose	2 mL	AIN457 for PK	15	5
Week 96	Pre-dose	2 mL	AIN457 for PK	16	5
Week 100	Pre-dose	2 mL	AIN457 for PK	17	5
Week 104 	Pre-dose	2 mL	AIN457 for PK	18	5
Week 108	Pre-dose	2 mL	AIN457 for PK	19	5
Week 112	Pre-dose	2 mL	AIN457 for PK	20	5
Week 116 	Pre-dose	2 mL	AIN457 for PK	21	5
Week 120	Pre-dose	2 mL	AIN457 for PK	22	5
Week 124	Pre-dose	2 mL	AIN457 for PK	23	5
Week 128 	Pre-dose	2 mL	AIN457 for PK	24	5
Week 132	Pre-dose	2 mL	AIN457 for PK	25	5
Week 136	Pre-dose	2 mL	AIN457 for PK	26	5
Week 140 	Pre-dose	2 mL	AIN457 for PK	27	5
Week 144	Pre-dose	2 mL	AIN457 for PK	28	5
Week 148	Pre-dose	2 mL	AIN457 for PK	29	5
Week 152	Pre-dose	2 mL	AIN457 for PK	30	5
Week 156 	Pre-dose	2 mL	AIN457 for PK	31	5
Week 260 	672 hours*	2 mL	AIN457 for PK	32	5
Week 268  (F8)	2016 hours*	2 mL	AIN457 for PK	33	5

The data and sample numbering for Week 52 visit (randomization) will have been collected as part of the end of maintenance visit (Week 52) from core study (e.g., CAIN457A2302 or CAIN457A2303)

The PK blood sampling at these time point must be collected for all subjects. PK blood collections at the other time points are “event driven” i.e., PK blood samples will only be collected in case of relapse.

\*Scheduled post-dose time points for sample numbers 32 and 33 (672 hours and 2016 hours post-dose, respectively) refer to the last dose given at Week 256 as time 0.

\*\*If a PK sample is collected at an unscheduled visit, the sample numbers will follow the pattern 1001, 1002 etc.

**Table 13-2 Blood collection log for IG**

Visit Name	Time point	Volume (approx.)	Analyte	IG collection number**
Week 52 	Pre-dose	(2 mL)	anti-AIN457 for IG	(503a)
Week 76	Pre-dose	2 mL	anti-AIN457 for IG	504
Week 104	Pre-dose	2 mL	anti-AIN457 for IG	505
Week 128	Pre-dose	2 mL	anti-AIN457 for IG	506
Week 140	Pre-dose	2 mL	anti-AIN457 for IG	507
Week 156	Pre-dose	2 mL	anti-AIN457 for IG	508
Week 260	672 hours*	2 mL	anti-AIN457 for IG	509
Week 268 (F8)	2016 hours*	2 mL	anti-AIN457 for IG	510

The data and sample numbering for Week 52 visit (randomization) will have been collected as part of the end of maintenance visit (Week 52) from core study (e.g., CAIN457A2302 or CAIN457A2303)

\* Scheduled post-dose time points for sample numbers 509 and 510 (672 hours and 2016 hours post-dose, respectively) refer to the last dose given at Week 256 as time 0.

\*\* If a IG sample is collected at an unscheduled visit, the sample numbers will follow the pattern, 3001, 3002, etc.

### **13.3 Appendix 3: Pharmacokinetics (PK) and immunogenicity (IG) sample labeling information**

#### **13.3.1 PK sample handling**

The samples must be labeled as in the following example and as provided by the central laboratory

Study code: CAIN457A2302E1

Site: cccc (4 digits for the current site number)

Subject: Cccerrr (4 digits for the site number where the subject was randomized concatenated with 3 digits for the assigned subject number. Add '0' ahead of the numbers if needed to obtain the correct number of total digits)

Sample number: As indicated in [Table 13-1](#)

Analyte: AIN457 for PK

Labels will be provided by the central laboratory with all information preprinted.

As PK samples are managed by a central laboratory, no added label should cover the original label.

#### **13.3.2 IG sample handling**

The samples must be labeled as in the following example and as provided by the central laboratory

Study code: CAIN457A2302E1

Site: cccc (4 digits for the current site number)

Subject: Cccerrr

(4 digits for the site number where the subject was randomized concatenated with 3 digits for the assigned subject number. Add '0' ahead of the numbers if needed to obtain the correct number of total digits)

Sample number: As indicated in [Table 13-2](#)

Analyte: anti-AIN457 for IG

Labels will be provided by the central laboratory with all information preprinted.

As IG samples are managed by a central laboratory, no added label should cover the original label.

# Document History – Major Changes compared to previous version of RAP module 3.

Version	Date	Changes
1.0	26-Jun-2017	First draft
2.0	31-Aug-2017	Second draft
1.0	15-Sep-2017	Final
Amendment 1.0	25-Oct-2017	Amylase and Lipase related criateria added in table 1-18

